5.8.3 Return or Destruction of Study Drug

At the completion of the study, there will be a final reconciliation of drug shipped, drug dispensed, drug returns, and drug remaining. This reconciliation will be logged on the drug reconciliation form, signed and dated. Any discrepancies noted will be documented and investigated, prior to destruction of unused study drug. Drug destroyed on site will be documented in the study files.

6 Study Procedures

Study related procedures include leukapheresis performed at baseline and at treatment completion..

Leukapheresis

Fenwal Amicus (Fenwal Inc., Lake Zurich IL, USA) apheresis systems (Version 3.1) will be used for mononuclear cell (MNC) collections. Access will be obtained using peripheral veins. Each subject will be evaluated after enrollment but prior to collection by the nursing staff of the Therapeutic Apheresis Treatment Unit to ensure that they have adequate venous access for the collection procedure. Venous access will consist of a 16 gauge steel needle placed into a vein in an antecubital fossa of one arm as a draw. The return will consist of an IV placed in the opposite arm. All MNC collections will have an endpoint of four hours processing time. Anticoagulant will be acid-citrate-dextrose solution-A (ACD-A) (Baxter Healthcare Corp., Deerfield, IL, USA) for subjects with a contraindication to heparin or a mixture of ACD-A, normal saline, and heparin for subjects without a contraindication to heparin. The heparin/ACD-A anticoagulant is preferred due to the lower incidence of citrate toxicity because of the lower citrate dose administered during the procedure. The lower dose of heparin administered also minimizes the length of systemic anticoagulation. The MNC offset will be 1.5 ml. The RBC offset start at 5.0 ml and will be adjusted during the procedure. The operator will observe the first cycle MNC transfer to determine if the RBCs pass completely through the right cassette. If the RBCs did not reach the top of the cassette, the operator will increase the RBC offsets to the next level for each succeeding cycle until the RBCs reached the top of the right cassette. Once the RBCs reach the top of the right cassette, no further adjustment will be made. If the subject's pre-procedure PLT count is $\geq 300 \times 10^9/L$, then the RBC offset will started at 6.0 ml. Only PBMCs will be harvested by this procedure. Nearly all blood is returned to the patient with only a small amount of blood lost in the process and in the tubing. PBMCs harvested by apheresis will be stored and used in

associated laboratory assays in the [name] HIV Immunology Laboratory BSL-3 facility on Guggenheim 5th floor in accordance with all appropriate Biosafety requirements.

Screening for peripheral neuropathy

Screening for peripheral neuropathy will occur at baseline (for study exclusion), and at each study visit (for safety monitoring), by administration of the European Organization for Research and Treatment of Cancer QLQ-CIPN20 Questionnaire. The 20-item CIPN-specific questionnaire which includes three scales assessing sensory (9 items), motor (8 items), and autonomic (3 items) symptoms and functioning with each item formatted the same as items of the EORTC QLQ-C30. It was developed to be used in conjunction with the EORTC QLQ-C30 following the EORTC guidelines for module development (15911236). The EORTC QLQ-CIPN20 has been tested in cancer patients receiving a variety of chemotherapies and has been shown to have internal consistency reliability based on Cronbach's alpha coefficients of 0.82, 0.73, and 0.76 for the three scales, respectively (PMID 23543373). The questions that comprise the QLQ-CIPN20 are listed in Appendix II. Any affirmative answer to questions in the QLQ-CIPN20 will trigger a further clinical assessment, and grading of suspected peripheral neuropathy according to the (CTCAE) Version 4.0 scale (Appendix I). Further clinical assessment of suspected peripheral neuropathy will be referred to a qualified physician in the area of drug-induced peripheral neuropathy.

The following toxicities will be considered to be dose limiting toxicities:

- Any \geq Grade 4 toxicity
- Any Grade 3 AE (except if there is clear evidence that it is not ixazomib related – i.e. a plausible alternative reason).
- Any \geq Grade 1 peripheral neuropathy (PN)

Specific management of toxicities in individual participants is discussed below.

Study related biology assays for the secondary outcomes include:

- CD4 T cell count, CD8 T cell count and CD4/CD8 ratio – by routine clinical flow cytometry (Mayo Medical Labs).
- Plasma HIV RNA viral load – by routine clinical RT-qPCR (Mayo Medical Labs).
- HIV Proviral DNA – by clinical qPCR (Mayo Medical Labs)
- Cell associated HIV DNA by digital droplet PCR – Peripheral blood CD4 T cells will be isolated from baseline and post-treatment leukapheresis samples by magnetic bead negative selection. Cell associated HIV DNA will be quantified by digital droplet PCR using RainDance™ ddPCR system ([name] HIV Laboratory).
- Culturable HIV – replication competent latent viral reservoir will be estimated using a quantitative viral outgrowth assay, considered the gold standard measurement, on peripheral blood CD4 T cells from baseline and post-treatment leukapheresis samples ([name] HIV Laboratory).

6.3 Visit 3 (Study Entry, Time 0 weeks)

- Obtain vital signs, including weight.
- Perform brief physical exam.
- Monitor for changes to concomitant drug and non-drug treatments
- Obtain CBC and an additional four (4) heparin tubes of whole blood for stored PBMC and plasma.
- QLQ-CIPN20 Questionnaire
- Prescribe study medication.

6.3.5 Visit 3.5 (Optional post-dose blood draw)

- Obtain four (4) heparin tubes of whole blood for stored PBMC and plasma.

6.4 Visit 4 (Treatment phase, Time 1 week \pm 3 days)

- Obtain vital signs, including weight.
- Perform brief physical exam.
- Monitor for changes to concomitant drug and non-drug treatments
- Obtain CBC and confirm lack of hematologic toxicity prior to administering day 8 dose.
- QLQ-CIPN20 Questionnaire
- Monitor and record adverse events
- Prescribe study medication.

6.5 Visit 5 (Treatment Phase, Time 2 weeks \pm 3 days)

- Obtain vital signs, including weight.
- Perform brief physical exam.
- Monitor for changes to concomitant drug and non-drug treatments.
- Obtain CBC and confirm lack of hematologic toxicity prior to administering day 15 dose.
- Obtain electrolytes, glucose, creatinine, LFTs.
- QLQ-CIPN20 Questionnaire
- Monitor and record adverse events
- Prescribe study medication

6.6 Visit 6 (Treatment phase, Time 3 weeks \pm 3 days)

- Obtain vital signs, including weight.
- Perform brief physical exam.
- Monitor for changes to concomitant drug and non-drug treatments
- Obtain CBC, CD4 and CD8 count, and confirm lack of hematologic toxicity.
- QLQ-CIPN20 Questionnaire
- Monitor and record adverse events
- Prescribe study medication.

6.7 Visit 7 (Treatment Phase, Time 4 weeks \pm 3 days)

- Obtain vital signs, including weight.
- Monitor for changes to concomitant drug and non-drug treatments.
- Monitor and record adverse events.
- Perform brief physical exam.
- Obtain CD4 and CD8 count, HIV RNA viral load, HIV proviral DNA, and an additional four (4) heparin tubes of whole blood for stored PBMC and plasma.
- Obtain electrolytes, glucose, creatinine, LFTs
- Obtain CBC and confirm lack of hematologic toxicity prior to starting next 28 day cycle.
- QLQ-CIPN20 Questionnaire
- Prescribe study medication.

6.8 Visit 8 (Treatment Phase, Time 6 weeks \pm 3 days)

- Obtain vital signs, including weight.
- Monitor for changes to concomitant drug and non-drug treatments.
- Monitor and record adverse events.
- Perform brief physical exam
- Obtain CBC, electrolytes, glucose, creatinine, LFTs
- Prescribe study medication. QLQ-CIPN20 Questionnaire
- Draw ixazomib trough level (pre dose sample for drug level determination) and 1 hour post-dose level.

6.9 Visit 9 (Treatment Phase, Time 8 weeks \pm 3 days)

- Obtain vital signs, including weight.
- Monitor for changes to concomitant drug and non-drug treatments.
- Monitor and record adverse events.
- Perform brief physical exam.
- Obtain CBC, CD4 and CD8 count, HIV RNA viral load, HIV proviral DNA and an additional four (4) heparins tube of whole blood for stored PBMC and plasma.
- Obtain electrolytes, glucose, creatinine, LFTs
- QLQ-CIPN20 Questionnaire
- Prescribe study medication.

6.10 Visit 10 (Treatment Phase, Time 12 weeks \pm 3 days)

- Obtain vital signs, including weight.
- Monitor for changes to concomitant drug and non-drug treatments.
- Monitor and record adverse events.
- Perform brief physical exam.
- Obtain CBC, CD4 and CD8 count, HIV RNA viral load, HIV proviral DNA and an additional four (4) heparin tubes of whole blood for stored PBMC and plasma.
- Obtain electrolytes, glucose, creatinine, LFTs
- QLQ-CIPN20 Questionnaire
- Prescribe study medication.

6.11 Visit 11 (Treatment Phase, Time 16 weeks \pm 3 days)

- Obtain vital signs, including weight.
- Monitor for changes to concomitant drug and non-drug treatments.
- Monitor and record adverse events.
- Perform brief physical exam.
- Obtain CBC, CD4 and CD8 count, HIV RNA viral load, HIV proviral DNA and an additional four (4) heparin tubes of whole blood for stored PBMC and plasma.
- Obtain electrolytes, glucose, creatinine, LFTs
- QLQ-CIPN20 Questionnaire
- Prescribe study medication.

6.12 Visit 12 (Treatment Phase, Time 20 Weeks \pm 3 days)

- Obtain vital signs, including weight.
- Monitor for changes to concomitant drug and non-drug treatments.
- Monitor and record adverse events.
- Perform brief physical exam.

- Obtain CBC, CD4 and CD8 count, HIV RNA viral load, HIV proviral DNA and an additional four (4) heparin tubes of whole blood for stored PBMC and plasma.
- Obtain electrolytes, glucose, creatinine, LFTs
- QLQ-CIPN20 Questionnaire
- Prescribe study medication.

6.13 Visit 13 (Leukapheresis, Time 22 weeks \pm 3 days)

- Leukapheresis performed at Clinical Apheresis Unit, Charlton 8th floor.
- Monitor and record adverse events.
- Obtain CBC.
- Draw ixazomib trough level (pre dose sample for drug level determination) and 1 hour post-dose level.

6.14 Visit 14 (Treatment Completion, Time 24 weeks \pm 3 days)

- Obtain vital signs, including weight.
- Monitor for changes to concomitant drug and non-drug treatments.
- Monitor and record adverse events.
- Perform brief physical exam.
- Obtain CBC, CD4 count, HIV RNA viral load, HIV proviral DNA and an additional four (4) heparin tubes of whole blood for stored PBMC and plasma.
- Obtain electrolytes, glucose, creatinine, LFTs
- QLQ-CIPN20 Questionnaire
- Obtain ECG.

6.15 Visit 15 (Final Study Visit, Time 28 weeks \pm 3 days)

- Obtain vital signs, including weight.
- Monitor for changes to concomitant drug and non-drug treatments.
- Monitor and record adverse events.
- Perform brief physical exam.
- Obtain CBC, CD4 count, HIV RNA viral load, HIV proviral DNA
- Obtain electrolytes, glucose, creatinine, LFTs QLQ-CIPN20 Questionnaire

6.16 Table 1. Table of Study Activities

Study Activity	V 1	V 2	V 3 ^c	V 3.5	V 4	V 5	V 6	V 7	V 8	V 9	V 10	V 11	V 12	V 13	V 14	V 15
Eligibility Screening	X															
Peripheral Neuropathy self-reported questionnaire	X		X		X	X	X	X	X	X	X	X	X		X	X
Informed consent	X															
Medical History	X		X		X	X	X	X	X	X	X	X	X		X	X
Concurrent meds	X															
Complete physical exam	X															
Brief physical exam			X		X	X	X	X	X	X	X	X	X		X	X
Vital Signs	X		X		X	X	X	X	X	X	X	X	X		X	X
CD4/CD8 T cell counts	X						X	X		X	X	X	X		X	X
HIV RNA Viral load	X							X		X	X	X	X		X	X
HIV Proviral DNA	X							X		X	X	X	X		X	X
CBC w/diff, platelet ^a	X		X		X	X	X	X	X	X	X	X	X	X	X	X
Heparin tubes for PBMC and plasma storage	X		X	X				X		X	X	X	X		X	
Serum chemistry ^b	X					X		X	X	X	X	X	X		X	X
Pre- and post-dose ixazomib level									X					X		
Adverse event evaluation					X	X	X	X	X	X	X	X	X		X	X
Urine Pregnancy test	X															
Leukapheresis		X												X		

a – Increased blood draw frequency may be required in the presence of hematologic toxicity. This will occur prior to each dose of ixazomib. In addition, increased blood draw frequency may be required if ixazomib is dosed weekly uninterrupted in Cycles 4-6.

b - Potassium, Creatinine, Alkaline phosphatase, ALT, AST, Total bilirubin, Direct bilirubin, Sodium, BUN, glucose, Chloride, Bicarbonate.

c- Visits 1 and 2 can occur on the same date, as long as they occur before visit 3.

6.17 Table 2: Instructions for treatment delays and dose reductions prior to ixazomib administration

CTCAE System/Organ/Class (SOC)	ADVERSE EVENT	AGENT	ACTION**
BASED ON INTERVAL ADVERSE EVENT			

CTCAE System/Organ/Class (SOC)	ADVERSE EVENT	AGENT	ACTION**
Investigations	Grade 2 thrombocytopenia (PLT count <75,000 - 50,000/mm ³) and/or neutropenia <1500 - 1000/mm ³	Ixazomib	Ixazomib dose should be omitted until the PLT and/or ANC has recovered to baseline values (counts >lower limit of normal). Ixazomib may be reinitiated at the same dose if the recovery has occurred in less than 7days. If the abnormality lasts ≥7 days or recurs, then the dose of ixazomib should be reduced by one dose level. If a patient is already at the lowest dose level, ixazomib should be permanently discontinued. Patients should have CBC checked weekly until resolution of abnormality.
	≥Grade 3 thrombocytopenia and/or neutropenia		Permanently discontinue ixazomib
	≥Grade 2 increase in AST, ALT or total bilirubin	Ixazomib	Ixazomib dose should be omitted until the abnormal LFT has recovered to baseline values. Ixazomib may be reinitiated at the same dose if the recovery has occurred in less than 7days. If the abnormality lasts ≥7 days or recurs, then the dose of ixazomib should be reduced by one dose level. If a patient is already at the lowest dose level, ixazomib should be permanently discontinued. Patients should have LFTs checked weekly until resolution of abnormality.
Skin and subcutaneous tissue disorders	Any Grade ≤2 Rash	Ixazomib	Omit ixazomib until rash resolves. Restart at same dose. If the rash recurs, reduce dose by one dose level. If a patient is already at the lowest ixazomib dose, ixazomib should be permanently discontinued.
	Any rash, ≥Grade 3	Ixazomib	Ixazomib should be permanently discontinued.

CTCAE System/Organ/Class (SOC)	ADVERSE EVENT	AGENT	ACTION**
Nervous System Disorders	Grade 1 peripheral neuropathy	Ixazomib	Ixazomib should be permanently discontinued.
Other	Any Grade 3 AE (except if there is clear evidence that it is not ixazomib related – i.e. a plausible alternative reason).	Ixazomib	Permanently discontinue ixazomib.
	Grade 4 AE	Ixazomib	Permanently discontinue ixazomib
	Plasma HIV RNA >500copies/ml on 2 consecutive occasions. (except if there is clear evidence that it is not ixazomib related – i.e. a plausible alternative reason – for example missed ART doses).	Ixazomib	Permanently discontinue ixazomib. Perform HIV genotypic resistance testing.

Use the NCI Common Terminology Criteria for Adverse Events (CTCAE) version 4.0* unless otherwise specified for all Adverse Events.

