4.4 Early Withdrawal of Subjects

4.4.1 When and How to Withdraw Subjects

Permanently discontinue ixazomib in individual subjects if any of the following occur:

- Death of any subject
- Anaphylactic reaction in any subject
- A life-threatening adverse event in any subject
- Any Grade 3 AE (except if there is clear evidence that it is not study drug related – i.e. a plausible alternative reason).
- Any Grade 4 AE
- A decrease in CD4 count below 350 cells/mm³, confirmed on repeat testing within 2 weeks, and associated with a relative drop in CD4 T cell percentage by >25% from baseline values, in the absence of an alternative explanation
- Confirmed virologic rebound (HIV-1 RNA >500 copies/ml confirmed by a second assay done within 14 days of the initial one). If the HIV-1 viral load is >20 copies/mL and <500 copies/mL, the HIV-1 viral load will be rechecked every 2 weeks until it becomes <20 copies/mL or >500 copies/mL.
- Development of \geq Grade 1 peripheral neuropathy with or without pain

An independent Data Safety and Monitoring Board will review the case. The committee and principal investigators will determine whether there is an association between the event and the ixazomib. The DSMB will make a recommendation accordingly as to whether the study should proceed, or if a modification in trial design is required, or if a replacement subject should be enrolled at the same dose as the withdrawn subject.

Reasons for early withdrawal of individual subjects may include:

- Subjects refuse to return for any remaining study visits.
- Subjects discontinue the ixazomib at any time during the study.
- Safety reasons, either at the discretion of the Investigator or at the subject's request.
- Protocol violations at the discretion of the principal investigators.
- Initiation of concomitant therapy that could interfere with the results of the study or ixazomib
- Subject's decision to withdraw, at any time.

All subjects are free to withdraw from participating in this study at any time and for whatever reason, specified or unspecified, and without prejudice.

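### Table 2's liver-test row has no upper grade limit, so it offers restart after severe rises for which Section 4.4.1 requires permanent discontinuation

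*Combined protocol and SAP*

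**What the plan says.** Section 6.17, Table 2 sets out what to do before each dose. Its liver-test row is triggered by "≥Grade 2 increase in AST, ALT or total bilirubin". The drug is held until the abnormal test has returned to baseline. Then:

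- Short rise: "Ixazomib may be reinitiated at the same dose if the recovery has occurred in less than 7days".
- Long or recurrent rise: "If the abnormality lasts ≥7 days or recurs, then the dose of ixazomib should be reduced by one dose level". A participant already at the lowest level stops for good.
- Monitoring: "Patients should have LFTs checked weekly until resolution of abnormality".

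Section 4.4.1 governs withdrawal. It opens with "Permanently discontinue ixazomib in individual subjects if any of the following occur", and its list includes every Grade 4 event, without exception, and "Any Grade 3 AE (except if there is clear evidence that it is not study drug related" (the bracket goes on to give a plausible alternative reason as the example). The rows of Table 2 labelled Other repeat both rules. Their Grade 3 entry reads "Any Grade 3 AE (except if there is clear evidence that it is not ixazomib related", and both rows order a permanent stop.

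Two other entries in Table 2 also use a hold-and-restart approach. The cytopenia entry is capped at Grade 2 and followed by a permanent-stop row for "≥Grade 3 thrombocytopenia and/or neutropenia". The rash entry is capped at Grade 2 and followed by a permanent-stop row for Grade 3 and above.

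**The concern.** Because the liver-test trigger has a floor but no ceiling, Grade 3 and Grade 4 rises fall inside it. The row's only route to permanent discontinuation depends on dose level and not on severity. Yet Section 4.4.1 and the Other rows end treatment for a Grade 4 rise and for a Grade 3 rise that is not clearly unrelated to ixazomib. The protocol therefore gives two answers for the same event.

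What is at stake is participant safety and consistent handling. Table 2 is the page consulted at the moment of dosing. Someone who finds the liver-test row there and follows it could give ixazomib again after a severe liver-test rise. Section 1.4 says there is no published experience with this drug in HIV-positive people, and Section 1.5 does not expect individual participants to gain from treatment.

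**Working it through.** No figure in the plan is in question. The check is a comparison of the rules, case by case.

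**Step 1: is a liver-test rise an adverse event at all?** Section 8.1 counts an abnormal laboratory value as an adverse event when, among other triggers, it delays treatment. The liver-test row itself requires dosing to be held. A Grade 3 or 4 rise handled under that row is therefore an adverse event, and Section 4.4.1 applies to it.

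**Step 2: the outcome under each provision.**

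| Rise in AST, ALT or bilirubin | Liver-test row, after return to baseline | Section 4.4.1 and Other rows | Agree? |
|---|---|---|---|
| Grade 2 | Restart path | No stop required | Yes |
| Grade 3, clearly unrelated | Restart path | Exempt from stop | Yes |
| Grade 3, not clearly unrelated, under 7 days | Same dose permitted | Permanent stop | No |
| Grade 3, not clearly unrelated, 7 days or more or recurrent, above lowest level | One level lower | Permanent stop | No |
| Grade 3, not clearly unrelated, 7 days or more or recurrent, at lowest level | Permanent stop | Permanent stop | Yes |
| Grade 4, under 7 days | Same dose permitted | Permanent stop | No |
| Grade 4, 7 days or more or recurrent, above lowest level | One level lower | Permanent stop | No |
| Grade 4, 7 days or more or recurrent, at lowest level | Permanent stop | Permanent stop | Yes |

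The provisions diverge in four of the eight cases.

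**Step 3: is the open upper limit deliberate?** Of the three hold-and-restart entries (cytopenia, liver tests, rash), two are capped at Grade 2 and paired with a stop row for Grade 3 and above. The liver-test entry has neither. No text exempts liver tests from Section 4.4.1. A drafting slip is the likelier explanation.

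**Step 4: who could be affected?** Taking the dose levels to be the group doses in Section 5.2, the lowest is 1 mg (Group 1, 3 participants). The same-dose restart could arise at any level, so for any of the maximum of 17. The reduced-dose restart can arise only above 1 mg, so for at most 17 − 3 = 14. These are ceilings on who is exposed to the wording, not expected events.

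**The case against.** The strongest reply is that the protocol already answers the question. Permanent discontinuation is ordered explicitly in two places, Section 4.4.1 goes on to let the DSMB replace the withdrawn participant, and Section 6 lists these same events as dose-limiting. Sections 4.4.1 and 9.3 send such cases to the board, and Section 7.2 brings cohort review forward after a dose-limiting toxicity. All of this stands and lowers the risk. It does not remove the row's contrary instruction. The board recommendations named concern whether the study proceeds, a design change or a replacement participant; none addresses re-dosing the person affected.

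A reader might infer that the investigator faces two irreconcilable orders, so that no action complies with both. The text does not establish that. The under-7-day limb is permissive. The other limb can fairly be read as setting the dose for a permitted restart, not as a duty to re-dose. On that reading, stopping breaches nothing. Nor does the row allow dosing through a severe rise, because any restart follows return to baseline.

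It is also tempting to say that the reduced-dose limb would be the usual one. Scheduled chemistry (Table 1) falls at weeks 2, 4, 6, 8, 12, 16, 20, 24 and 28, so with ±3-day windows the shortest gap is 14 − 3 − 3 = 8 days. But that inference assumes the 7 days run from detection and that nobody retests early. The protocol fixes neither, and it gives no recovery data.

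It can be said that Table 2 was never meant to stand alone: its neuropathy row names only Grade 1 and leaves higher grades to other provisions. That is fair, but the neuropathy row is silent on higher grades, whereas the liver-test row covers them and gives a different action. Reading the Other rows as residual would ease the conflict within Table 2 but not the conflict with Section 4.4.1.

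Finally, the heading of the Action column carries a double asterisk with no matching note in the available text. A note on precedence may have been lost, so the absence of one is stated only for the visible text.

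**Conclusion.** Wrong as written: an internal contradiction that bears on participant safety and is cheap to correct. For a Grade 4 liver-test rise, or a Grade 3 rise not clearly unrelated to ixazomib, Table 2's liver-test row offers restart after recovery, while Section 4.4.1 and the table's Other rows require a permanent stop.

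The size is unknown, because the documents give no rate of liver-test events. A reader might also suppose that the error distorts the trial's results. It does not. The Section 6 list and the Other rows already capture these Grade 3 and 4 events for escalation, and the primary analysis (Section 7.2) describes adverse event rates by grade whatever dosing decision follows.

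The conclusion rests on two assumptions: that a rise which holds dosing is an adverse event under Section 8.1, and that no missing footnote settles precedence. It does not depend on reading the reduced-dose limb as mandatory.

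**What to change.** Make two edits to Table 2:

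1. Narrow the liver-test trigger and keep its present action: *Grade 2 rise in AST, ALT or total bilirubin, or a Grade 3 rise clearly shown not to be due to ixazomib.* The exempt Grade 3 rise must be named, because a bare cap at Grade 2 would leave it without a dosing path.
2. Add a row beneath it: *Grade 3 rise in AST, ALT or total bilirubin, unless clearly shown not to be due to ixazomib, or any Grade 4 rise: stop ixazomib permanently.*

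This brings the table into line with what Section 4.4.1 already requires. The cost is amendment wording only, with no added visits, tests or participants.

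Two optional clarifications could go in the same amendment. Section 5.3 could point to the dose-limiting toxicity list in Section 6 instead of to Table 2. In Section 6.21, the sentence on restarting at a reduced level, which follows the Grade 3 rash text, could refer the reader to Table 2, which stops the drug at that grade.
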